## VI. BIOSTATISTICAL ANALYSIS

Data forms and questionnaires will be coded in a standardized manner, and double-entered into our database. Digital measures/recordings will be similarly tracked in our database and regularly backed up. Analyses will be conducted using standard statistical software such as SAS and Matlab.

### Sample size calculation:

To calculate the sample size for our primary outcome PLP as measured by a visual analogue scale (VAS), we used the study from Soler et al. as a reference “Effectiveness of transcranial direct current stimulation and visual illusion on neuropathic pain in spinal cord injury”. Using VAS as the basis for the calculation and considering results from this study: a mean and standard deviation of 5.2 ( $\pm 1.5$ ) in experimental group (tDCS + visual illusion) and 6.4 ( $\pm 1.6$ ) in control group (visual illusion), and using a bidirectional alpha of 0.05 and power of 80%, we would need a total sample of 108 subjects (27 subjects in each group). Additionally, estimating a conservative attrition rate of 20%, our sample size would be 132 subjects.

Although we calculated the sample for our primary aim, it is important to underscore that power calculation will be adequate also for our secondary aim measuring neurophysiological outcomes. In fact, neurophysiological outcomes usually have less variability thus need smaller sample sizes to show significant differences. In fact as shown in our preliminary data and also from data from other studies [58, 59] effect sizes from TMS data will be larger and for the fMRI, we expect BOLD changes in sensory motor cortex around 3 to 5% (as shown by previous studies [56]) – therefore a sample of 7 to 8 subjects will be enough to detect significant changes.

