## II. SPECIFIC AIMS

The specific aims of this experiment are as follows:

[figure not shown]
- **Aim 1: To evaluate the efficacy of tDCS and mirror therapy (MT) as rehabilitative tools for the management of chronic PLP patients.**

We will explore the aim 1 in a randomized factorial controlled trial in which patients will be assigned to one of four groups: active tDCS and active MT; sham tDCS and active MT; active tDCS and sham MT (which consists of using a covered mirror for the therapy); and both sham tDCS and sham MT (covered mirror).

The primary end point will be severity of pain measured by changes in PLP as indexed by a Visual Analog Scale (VAS). The study will require a total of 13 weeks to be completed. The first week, each patient will give daily reports of their pain using a VAS, accounting for their PLP experience in the past 24hs. This initial baseline week will be followed by 4 weeks of treatment (tDCS and/or MT) and a final 8-week follow-up period without any treatment to examine long-lasting effects of each therapy. *Our hypothesis is that the combined intervention (tDCS and MT) will result in a greater pain reduction as compared with any therapy alone and no therapy.*

- **Aim 2: To examine the mechanisms underlying PLP using two neurophysiological techniques.**

For each of the four groups described in aim 1, we will determine the neural correlates of the effect. We will use single-pulse and paired-pulse transcranial magnetic stimulation (TMS) to assess cortical mapping and cortical excitability changes associated with cortical reorganization. We will also use functional magnetic resonance imaging (fMRI) to assess brain changes, including the quantification of maladaptive cortical reorganization. Using fMRI, we will determine the changes in Blood-Oxygen-Level dependent activation between the sensory-motor cortex of the affected and unaffected side after the treatment. We will compare these neurophysiological parameters before and after treatment in each of the four groups. *Our hypothesis is that the combined group (tDCS and mirror therapy) will have a greater activation than any therapy alone and also than the no therapy group (sham tDCS and covered mirror). This effect will also be correlated with pain reduction.*

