#### *For aim 1:*

[figure not shown]
The primary outcome is PLP indexed by VAS. PLP will be analyzed using intensity of pain over time. To analyze these data, we will initially build a mixed ANOVA model in which the dependent variable will be the outcome of PLP (such as VAS) and the independent variables will be group (active tDCS-MT; sham tDCS-MT; active tDCS and covered MT; sham tDCS- covered MT), time (baseline and after treatment and follow-up) and the interaction group\*time. In addition we will add the random variable ID to account for within subject’s variability and the repeated measures on time. We will initially perform this full model and, subsequently, post-hoc comparisons with corrections for multiple comparisons will be carried out initially to test our main hypotheses. Furthermore we will test the correlation in improvement between outcomes using Pearson’s correlation tests. P-values for secondary and exploratory outcomes will be determined without corrections for multiple comparisons. Finally we will apply a path analysis [60, 61] to the primary outcome data to determine if pain reduction associated with the combined intervention (tDCS and MT) is due to direct effects versus indirect effects through improvement in secondary outcomes. We propose that a direct effect of tDCS and MT on pain can be assumed if the treatment effect cannot be explained by changes in psychological or functional outcomes. Statistical models for pain will be developed using covariates that include site center, baseline

[figure not shown]
pain, psychological changes, functional changes, and the covariate treatment (main effect of treatment). To complete the path analysis separate regression models will be run to model the effects' of treatment on each outcome alone including all the secondary outcomes. Analyses of the secondary outcomes will be conducted in an exploratory manner (no correction for multiple comparisons). For the intention-to-treat analysis, we will use a conservative method and assume that participants will not improve from the last measured point. But we will also perform a sensitive analysis for the missing data using other methods such as completers only.

*For aim 2:*

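### The 80% power is for one contrast at an uncorrected 0.05, so it is not shown for the multiplicity-corrected comparisons that test Aim 1

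*Combined protocol and SAP*

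**What the plan says.** Section VI, Sample size calculation, takes post-treatment VAS values from a reference study in spinal cord injury: 5.2 (SD 1.5) with tDCS plus visual illusion, and 6.4 (SD 1.6) "in control group (visual illusion"). It then states that "using a bidirectional alpha of 0.05 and power of 80%, we would need a total sample of 108 subjects (27 subjects in each group"), and that, "estimating a conservative attrition rate of 20%, our sample size would be 132 subjects", which is 33 per arm.

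Section II, Aim 1, hypothesises that the combined intervention "will result in a greater pain reduction as compared with any therapy alone and no therapy". With four arms, that is three contrasts of the combined arm: against MT alone, against tDCS alone, and against double sham.

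Section VI, Statistical Analysis for aim 1, fits a mixed ANOVA with group, "time (baseline and after treatment and follow-up") and their interaction. After that model, "post-hoc comparisons with corrections for multiple comparisons will be carried out initially to test our main hypotheses". For intention to treat, the plan will "assume that participants will not improve from the last measured point". It will also "perform a sensitive analysis for the missing data using other methods such as completers only".

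The documents do not name the correction, the number of comparisons or the primary visit. They give no assumed difference for combined against tDCS alone or against double sham, and no correlation between visits.

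**The concern.** The sizing and the analysis use different significance levels. The sizing spends the full two-sided 0.05 on one contrast, while the analysis plans several contrasts with a correction. Under a correction such as Bonferroni or Holm, the same contrast faces a stricter threshold for at least part of the time, and the calculation makes no allowance for that. Two of the three hypothesised contrasts have no stated effect at all.

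This is the only power figure given for Aim 1. If the combination fails to separate from a single therapy after correction, a reader cannot tell from the plan what difference the trial was able to detect. Leaving the contrasts, correction and visit open also allows those choices to be made after the data are seen.

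**Working it through.** **Inputs from the sample size section.** Means 5.2 and 6.4, so the difference is d = 1.2. SDs 1.5 and 1.6, so the pooled variance is (1.5² + 1.6²)/2 = (2.25 + 2.56)/2 = 2.405 and s = 1.551. Alpha is 0.05 two-sided and target power is 80%.

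**1. The plan's own figure.** n per arm = 2(z₀.₉₇₅ + z₀.₈₀)² s²/d² = 2 × (1.960 + 0.842)² × 2.405/1.44 = 26.2, so 27 per arm and 4 × 27 = 108. The stated number reproduces, for one contrast with no correction. The enrolled number is 132/4 = 33 per arm; a 20% loss leaves 0.8 × 33 = 26.4, close to 27.

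**2. Power of that contrast by level.** The noncentral t test has noncentrality d/(s√(2/n)), which is 1.2/(1.551 × √(2/27)) = 2.84 at n = 27 and 3.14 at n = 33. The lower figure in each range uses two-sample degrees of freedom (2n − 2), the higher one the four-arm error term (4n − 4). Bonferroni over three tests at 0.05/3 = 0.0167.

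| Analysed per arm | Uncorrected 0.05 | Bonferroni over three |
|---|---|---|
| 27 | 79.7-80.4% | 64-66% |
| 33, no loss or dilution | 87-88% | 75-76% |

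**3. Holm over the three combined-arm contrasts.** This depends on the other two differences, which the documents do not give. The values below are assumptions. Simulation: 400,000 runs, normal arm means, four-arm error term; power is for combined against MT alone with d = 1.2.

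| Assumed difference vs tDCS alone | Assumed difference vs double sham | 27 per arm | 33 per arm, no loss or dilution |
|---|---|---|---|
| 1.2 | 1.2 | 74% | 83% |
| 1.2 | 2.4 | 77% | 85% |
| 0 | 1.2 | 69% | 79% |

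**4. Choices that move these figures.** All correlations here are assumptions; the power figures are at 27 per arm with the four-arm error term.
- A fixed sequence that starts with combined against MT alone tests it at the full 0.05, so that contrast keeps about 80%.
- Baseline adjustment by ANCOVA multiplies s by √(1 − r²). At r = 0.5, Bonferroni over three gives 80%.
- A change score multiplies s by √(2(1 − r)). At r = 0.3, power is 49% with Bonferroni over three and 66% even uncorrected.
- Averaging m post-treatment visits, if the 1.2 difference persists, multiplies s by √((1 + (m − 1)r)/m). Bonferroni over three then gives 80% (two visits) or 85% (three) at r = 0.5, and 74% or 77% at r = 0.7.

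**The case against.** The strongest reply is that the raw single-visit figures are not the planned analysis either. The plan analyses pain over time in a repeated-measures model, and averaging visits or adjusting for baseline could bring a corrected contrast back to 80%. This stands as a limit on the size of the problem. It does not rescue the stated figure, because the plan commits to neither choice and gives no correlation. Aim 1 also words the endpoint as change in pain, and a change score with low baseline correlation would lower power.

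A second reply is that 132 patients are enrolled and the intention-to-treat rule keeps them all. With 33 per arm and no dilution, Holm does exceed 80% in two of the three scenarios. But the plan expects 20% attrition, values carried forward for patients who leave may dilute the effect, and Bonferroni over three stays at 75-76%.

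A third reply is that Bonferroni is the pessimistic choice for three contrasts that share an arm. That is fair, and it is why the Holm figures are given beside it.

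A reader might go further and infer that the plan never tests the contrast it was sized on. That is not so: by the analogy above, combined against MT alone is one of the three hypothesised contrasts, and what demonstrably differs is its significance level. A reader might also infer that any multiplicity procedure takes this contrast below 80% at 27 per arm. The fixed sequence in the working shows otherwise.

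**Conclusion.** The mismatch is real: the sample size arithmetic is right for one uncorrected contrast, and 80% power is not shown for the corrected comparisons that test Aim 1. On the plan's own difference and SD, compared at a single visit with 27 per arm, power for the sized contrast falls from about 80% to 64-66% (Bonferroni over three) or 69-77% (Holm over three). At 33 per arm without loss or dilution, the corresponding figures are 87-88%, 75-76% and 79-85%.

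These ranges rest on three things: reading visual illusion as a stand-in for mirror therapy, which the plan does not spell out; a single-visit comparison; and, for Holm, assumed differences for the other two contrasts.

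It is tempting to conclude that the trial is underpowered or must enrol more patients. The documents do not support that. They leave the correction, the contrasts, the visit, the analysed number and the correlation open, and some combinations reach 80%. The finding is a gap in what has been shown. It should be fixed, since this is the only power figure for Aim 1.

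**What to change.** Keep N = 132. In the analysis section, name the confirmatory contrasts, the correction (for example Holm over the three contrasts of the combined arm) and the primary visit. Then restate power for that corrected analysis, giving the assumed difference for each contrast, the analysed number per arm (27 or 33, with any dilution from carried-forward values) and any correlation relied on.

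The cost is wording in the sample size and analysis sections, with no change to enrolment or visits. The downside is that the stated power will probably be less favourable than 80%.

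Making combined against MT alone the single primary contrast, or the first in a fixed sequence, is an option and not a requirement. It keeps about 80% for that contrast at 27 per arm under the raw 1.2-point assumption. As a single primary contrast, it leaves the other two hypotheses without a confirmatory test. In a fixed sequence, no later contrast can be claimed if the first one fails.

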### *Screening Procedures:*

At Screening the PI and/or a co-investigator will conduct, once more a review of inclusion/exclusion criteria to determine the subject's eligibility for enrollment. Study procedures will be reviewed with the subject, and documentation of informed consent will be obtained.

At Screening the following procedures will be completed:

- Discuss study-specific procedures with the subject.

- Review inclusion and exclusion criteria.
- Obtain a signed and dated consent form.
- Conduct a Demographics Survey, Brief Medical History and Beck depression inventory.
- fMRI screening questionnaire\*.
- Urine pregnancy exam (if applicable).

\* If the subject is not eligible for an fMRI at the time of the study we will not perform this assessment as fMRI is not required for study eligibility and it is only used as a secondary outcome.

Randomization:

Once eligibility and consent have been approved and completed, randomization will occur using the randomized list generated by an automatic web-base randomization program ([www.randomization.com](http://www.randomization.com)). Subjects will be randomly assigned to one of the four groups in a 1:1:1:1 allocation ratio. We will use stratified randomization methods with random block sizes of blocks of 4 and 8. Patients will be stratified based on their baseline pain levels (two strata: less or equal of average 6 in VAS or more than 6 in VAS) and by study center (IMREA or SRH-Neuromodulation Lab). Randomization order will be kept in sealed envelopes; therefore subjects will get their assignment according to the order of entrance in the study (for instance, subject 1 will be assigned the first envelope that will contain his/her assignment according to this block randomization list).

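### The 20% attrition allowance fits a completers analysis, but the ITT rule keeps dropouts at their last value, so the stated 80% power depends on an unstated assumption about when they leave

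*Combined protocol and SAP*

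**What the plan says.** Under Sample size calculation (section VI), the plan takes VAS means and SDs from a published study of tDCS with visual illusion: 5.2 (SD 1.5) in the experimental group and 6.4 (SD 1.6) in the control group. It continues "using a bidirectional alpha of 0.05 and power of 80"%, and concludes "we would need a total sample of 108 subjects (27 subjects in each group"). Attrition is then added: "estimating a conservative attrition rate of 20%, our sample size would be 132 subjects". Randomisation is equal across four arms, so 132 is 33 per arm. This section says nothing about the effect expected in those who drop out.

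Under Statistical Analysis, For aim 1, missing data are handled differently. For the intention-to-treat analysis, "we will use a conservative method and assume that participants will not improve from the last measured point". The plan adds a "sensitive analysis for the missing data using other methods such as completers only". The same section specifies a mixed model with group, time and their interaction, a random subject term and repeated measures on time.

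**The concern.** Enrolling extra subjects so that roughly the required number remains keeps the power only if the analysis uses those who remain and the full 1.2 points applies to them. The ITT rule does something else. It leaves all 33 per arm in the comparison but freezes dropouts at whatever they last reported. A subject who leaves before any benefit contributes no treatment difference, so the expected difference shrinks, and values stuck near baseline can widen the spread.

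The power statement and the missing-data rule therefore describe different analyses. At stake is whether the 80% holds for the ITT result. Early loss is possible, because the schedule asks for ten stimulation visits in the first two weeks. The documents do not say when dropout is expected or which time point carries the primary comparison.

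**Working it through.** **1. Reproduce the plan's figures.** Pooled variance = (1.5² + 1.6²)/2 = 2.405, so SD = 1.551; difference = 6.4 − 5.2 = 1.2.

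n per group = 2 × (1.960 + 0.842)² × 2.405 / 1.2² = 26.2, rounded up to 27; 4 × 27 = 108. This matches. Power at 27 per group is 81.1% (normal approximation) or 79.7% (t-test).

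Attrition: 27 × 1.2 = 32.4, rounded up to 33; 4 × 33 = 132. This matches.

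**2. Which analysis does the allowance protect?** After 20% loss, 33 × 0.8 = 26.4 completers per arm remain. At the full 1.2 points, power is 80.3% (normal) or 78.8% (t). The allowance is thus the one for a completers analysis.

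**3. Apply the ITT rule instead.** Let f be the share of the effect that dropouts have at their last measured point (not given in the documents; range 0 to 1), and B the baseline mean (also not given). With 20% dropout in each arm:

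- Expected difference = 1.2 × (0.8 + 0.2f).
- Variance in each arm = SD² + 0.2 × 0.8 × [(1 − f)(B − arm mean)]².

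Example, f = 0 and B = 6.4: difference 0.96; variances 2.25 + 0.16 × 1.2² = 2.480 and 2.56 + 0 = 2.56; pooled SD 1.588. Example, f = 0 and B = 7.5: variances 2.25 + 0.16 × 2.3² = 3.096 and 2.56 + 0.16 × 1.1² = 2.754; pooled SD 1.710.

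Power of a two-sided 0.05 t-test with 33 per arm:

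| Share kept, f | Difference | SD unchanged | B = 6.4 | B = 7.0 | B = 7.5 |
|---|---|---|---|---|---|
| 0 | 0.96 | 69.7% | 67.7% | 64.8% | 61.3% |
| 0.25 | 1.02 | 74.9% | 73.8% | 72% | 70.0% |
| 0.5 | 1.08 | 79.6% | 79.1% | 78.4% | 77.5% |
| 0.75 | 1.14 | 83.7% | 83.6% | 83.4% | 83.2% |
| 1 | 1.20 | 87.2% | 87.2% | 87.2% | 87.2% |

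B = 6.4 equals the planning mean of the control group, so it means no change in controls. The higher values of B are assumptions.

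**4. Break-even.** With the widened SD, 80% is reached at f = 0.55, 0.57 and 0.60 for B = 6.4, 7.0 and 7.5. With SD unchanged it is about 0.52 by t-test, and f = 0.5 already gives 80.8% by the normal approximation. So roughly 50-60% of the effect must be kept.

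**The case against.** The strongest reply is that the rule carries forward the last measured point, not baseline. Phantom limb pain is rated before and after every stimulation session, so a mid-treatment dropout keeps whatever benefit had accrued. Of the 13 weeks, 8 are follow-up without treatment, and someone lost then already has the after-treatment value and does not dilute that contrast. As an illustration under assumed timing, spread the 20% evenly over 13 weeks, with no effect in week 1, linear gain over the 4 treatment weeks and the effect held afterwards. The average share kept is (1 × 0 + 4 × 0.5 + 8 × 1)/13 = 0.77, and power is about 82-84% for B from 6.4 to 7.5. This stands: nothing in the documents makes the unfavourable half of the table more likely than the favourable half.

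Two further points stand. The 61% figure needs a baseline mean of 7.5, which the documents do not give; without a baseline above 6.4, the low end is about 68-70%. And the table is for one unadjusted two-group comparison, as in the plan's own calculation, not for the planned repeated-measures model with corrected post-hoc comparisons. The widening of the SD in particular need not carry over to that model.

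It can also be said that preferring an observed-data model is a matter of taste, since other missing-data methods are already planned as sensitivity analyses. This stands only in part: the plan would still quote 80% for an analysis other than its ITT rule, with no statement of what that requires.

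**Conclusion.** The mismatch is real. The allowance is computed for completers at the full effect, while the ITT analysis keeps dropouts at their last value. For the plan's own comparison, power under that rule runs from about 68-70% (none of the effect kept), through 78-80% (half) and 83-84% (three quarters), to about 87% (all). It falls to about 61% only with none kept and an assumed baseline mean of 7.5.

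A reader might infer that the trial is underpowered, with 61-79% in place of 80%. The documents do not support that: such a range stops at half the effect kept, leaves out the scenarios above 80%, and takes its lower end from an assumed baseline. What follows is narrower. The 80% is conditional on dropouts keeping roughly half or more of the effect, and the plan does not say so. All figures assume 20% dropout in each arm and the planning means and SDs.

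**What to change.** In the Aim 1 analysis text, make the primary ITT analysis the mixed model already specified there, fitted to all observed visits of all randomised subjects without single imputation. Keep both the last-measured-point rule and the completers analysis as sensitivity analyses. Dropouts then contribute what was observed and are not frozen at an early value. The cost is a change of wording and reliance on data being missing at random, which is why the carry-forward analysis should be retained.

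If the carry-forward rule stays primary, add to the sample size section that the 80% assumes dropouts keep roughly half or more of the effect, and give the range above with its assumptions. The cost is a less favourable power statement. Neither option needs added enrolment.

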#### IV. SUBJECT SELECTION

In this study, we will recruit 132 subjects with phantom limb pain (PLP) of traumatic etiology (congenital or diabetic amputees will be excluded since these patients may have a different neuroplastic profile). The subjects will be recruited by 2 main neurorehabilitation study centers, one at neuromodulation center - Spaulding rehabilitation Hospital and one at University of Sao

Paulo Brazil (IMREA). Subjects will need to meet all of the following inclusion criteria and none of the following exclusion criteria:

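### Enrolling 132 does not keep the required 108 evaluable subjects at the stated 20% attrition; it does so only up to about 18%

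*Combined protocol and SAP*

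**What the plan says.** Under Sample size calculation (section VI), the plan takes means and standard deviations of 5.2 (1.5) and 6.4 (1.6) from a published trial in spinal cord injury. Its error rates are set by "using a bidirectional alpha of 0.05 and power of 80" per cent. It concludes that "we would need a total sample of 108 subjects (27 subjects in each group").

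The next sentence makes the allowance for dropout: "estimating a conservative attrition rate of 20%, our sample size would be 132 subjects". No inflation formula is given.

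Section IV (Subject Selection) adopts the result as the recruitment target: "In this study, we will recruit 132 subjects with phantom limb pain (PLP) of traumatic etiology". Section V (Study Procedures) repeats it. Allocation is equal; under Screening Procedures the plan states: "Subjects will be randomly assigned to one of the four groups in a 1:1:1:1 allocation ratio". Hence 132 means 33 per arm.

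On subjects who leave early, the text for aim 1 under Statistical Analysis says of the intention-to-treat analysis: "we will use a conservative method and assume that participants will not improve from the last measured point". A completers-only analysis is added as a sensitivity analysis.

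**The concern.** An attrition allowance should be set so that the number left after the expected loss is the number the calculation asked for. That means dividing the required number by the retained fraction. Multiplying it by one plus the loss rate gives too small a total, because the loss applies to everyone enrolled and not only to those who finish.

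The plan's 132 looks like the product of multiplying. If so, the stated attrition rate, evaluable number and enrolment cannot all hold at once. The plan calls its 20% conservative, and 132 is the headline recruitment figure, so a reader would take it that 108 evaluable subjects are secured at that loss. They are not. What is at stake is the accuracy of that statement and, to a small degree, the power of an analysis restricted to completers.

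**Working it through.** **Inputs** (all from Sample size calculation unless noted)
- Difference in means: 6.4 − 5.2 = 1.2.
- Pooled SD: √((1.5² + 1.6²)/2) = √2.405 = 1.551. Standardised difference: 1.2/1.551 = 0.774.
- Two-sided alpha 0.05 and power 80%, giving normal quantiles 1.960 and 0.842.
- Attrition 20%; four equal arms (Screening Procedures, randomization paragraph).

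**Step 1. Reproduce the plan's 27 per group.** By the normal approximation, n = 2 × (1.960 + 0.842)² × 2.405 / 1.2² = 26.2, rounded up to 27 per group, and 4 × 27 = 108. This matches the plan exactly. The noncentral t calculation needs 28 per group (112 in total), so the plan's figure agrees with the normal approximation.

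**Step 2. Inflate for 20% attrition.**
- In total: 108/(1 − 0.20) = 135.
- By arm: 27/0.80 = 33.75, rounded up to 34, and 4 × 34 = 136.
- Stated: 132, which is 3 short of 135 and 4 short of 136.

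**Step 3. What 132 delivers.**
- Completers at 20% loss: 132 × 0.80 = 105.6, or 26.4 per arm, against 108 and 27.
- Largest loss that still leaves 108: (132 − 108)/132 = 24/132 = 18.2%.

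**Step 4. A possible origin of 132.** 27 × 1.2 = 32.4, rounded up to 33 per arm, and 4 × 33 = 132. This reproduces the figure exactly, but it is an inference because the plan does not state its formula. Steps 2 and 3 do not depend on it.

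**Step 5. Effect on power**, for one uncorrected two-arm comparison of completers. The normal approximation is Φ(0.774 × √(n/2) − 1.960); the second method is the noncentral t.

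| Completers per arm | Normal approximation | t test |
|---|---|---|
| 27 (plan's target) | 81.1% | 79.7% |
| 26.4 (20% loss from 33) | 80.3% | 78.8% |
| 26 (whole subjects) | 79.7% | 78.1% |

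Within either column, going from 27 to 26.4 costs about 0.9 points. Going from 27 to 26 costs about 1.5 points by the normal approximation and 1.6 by the t test.

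**The case against.** The strongest reply is that nothing of substance is lost. By the formula that yields 27 per group, the unrounded need is 26.2 per arm, or about 105 in total (4 × 26.2 = 104.8), and 105.6 remain after 20% loss. Rounding up left enough slack that power at that loss is still about 80%. This stands as a point about power. It does not rescue the sentence, because the plan names 108 as the number it needs and 132 does not preserve that number at the loss it names.

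A reader might infer from the t-test column that the attrition slip brings the stated 80% down to 78-79%. The documents do not support that. The 78-79% appears only on changing method, and by the t test 27 per arm is already at 79.7% with no shortfall in completers. The part due to the inflation is the drop within a column.

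A reader might also infer that the main analysis would rest on 105.6 subjects. As I read the text for aim 1, the intention-to-treat analysis carries the last measured point forward, so subjects who drop out with data remain in it. The 105.6 is the completers-only number. Carried-forward values may dilute the treatment difference, so this does not show that full power is kept.

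Finally, the planned analysis is a mixed model with repeated measures followed by corrected post-hoc comparisons, and not a single t test. The documents do not give what is needed to compute its power, and those features could outweigh a one-point difference. That is a good reason not to write a revised power figure into the plan.

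**Conclusion.** Wrong as written, minor. With 108 evaluable subjects required and 20% attrition, enrolment should be 135 (136 for four equal arms). The stated 132 is 3 to 4 short, about 2 to 3%, and supports an allowance of about 18%. This rests on the plan's own figures and on the ordinary reading of attrition as a fraction of those enrolled.

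The power consequence is about 1 to 1.6 points. It assumes the plan's 1.2-point difference, the pooled SD of 1.551, loss spread evenly over the arms, and a single uncorrected comparison of completers. It does not amount to a material loss of power and gives no reason to change the design.

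**What to change.** Keep 132 and replace the attrition sentence under Sample size calculation with one along these lines: *132 subjects retain 108 evaluable subjects (27 per group) at up to about 18% attrition.* That statement is true whichever power formula is used. The recruitment figures in sections IV and V stay as they are.

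The cost is one sentence and a slightly less favourable stated allowance. No extra enrolment is needed.
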